3.4.1 Sample Collections

Salivary samples and stool samples for clinical laboratory tests will be obtained according to the schedule of events table (Appendix 2). The list of clinical laboratory tests is in Appendix 3.

Scientific advances in metabonomics indicate that it may be possible to identify biomarkers that will allow a better understanding of the pathogenesis, diagnostics and treatments of COV+, and that are predictive of drug efficacy and toxicity for available therapies

3.5 Treatments

3.5.1 Method of Assigning Patients to Treatment Groups

All patients will be assigned to the treatment group for the first 10 patients treated with open label BSS. The Subsequent 50 patients (two groups of 25) will be randomized to either placebo or BSS. The patients will be assigned by coin-toss, heads to placebo and tails to active treatment (or other suitable randomization event) by a member of the research team not directly involved in the clinical trial.

3.5.3 Management of Clinical Supplies

Study medication should be securely stored as per manufacturers guidance until dispensed in accordance with the protocol.

Study medication will be dispensed at Baseline. Accurate, up-to-date records of all clinical supplies must be maintained. At the end of the study, the study site must be able to reconcile delivery records with those of received, dispensed, and returned study medication. Unused medication will be disposed in an environmentally responsible fashion. Written account of any discrepancies will be required.

3.5.4 Treatment Compliance

Patients should administer their study medication at approximately the same time each day. Patients will return all used and unused (if any) drug supplies at the end of the study.

3.5.5 Prior and Concomitant Therapy

Patients are restricted from taking any medications listed in the exclusion criteria or any other medications that, in the opinion of the Investigator or the Medical Monitor, may affect the safety profile of the study medication or interpretation of the results, except when such drugs are vital for the patient's welfare and/or no other drug is available. However, this may result in patient discontinuation from study participation (see Section 3.4, Removal of Patients from the Study).

Patients will be prohibited from taking the following medications during the study:

- Corticosteroids (including oral, IV, IM, or rectally administered) except those used in the treatment of COVID-19 infection
- · Chemotherapy agents
- Anti-diarrheals and anti-spasmodics Opiates can be used in hospitalized patients and with outpatients if they are prescribed to a patient
- Any investigational or marketed drugs that, in the opinion of the investigator, may interfere with the evaluation of the study medication.

3.6. Statistical Methods

3.6.1 Statistical Analysis Plan

Statistical Analysis Plan

Efficacy Analysis:

The primary efficacy analyses will be to compare the negative Saliva rates at Week 1, 2 and 3 between the SOC control group and the BSS + SOC treatment groups using the analysis of variance (ANOVA) with treatment group and baseline BMI as a covariate variable in the model. Clinical factors such as age, antibiotic use, number of recurrences, etc. will be examined for the impact on the treatment effect.

The analyses of the primary efficacy endpoint will be conducted to compare historical SOC control vs. BSS plus SOC groups. The ANOVA or a nonparametric method, whichever is appropriate, will be used to compare the rates of recurrence at each time point.

For categorical endpoints, chi-square test or a Fisher exact test (for 2x2 tables) will be used to assess treatment effect. For continuous endpoints, the ANOVA or a nonparametric method will be used, whichever is appropriate.

The comparability of patient's population at baseline will be assessed using either chisquare test (for categorical data) or t-test (for continuous variables).

Safety Analysis:

Intent-to-treat (ITT) patients who receive one dose of study drug will be included in the safety evaluation.

The number of AEs reported by patients, who participate in the study, as well as their causality and severity, will be summarized for each treatment group. Frequency tables for AEs by MedDRA terms will be presented. AEs will be assessed by age, sex, and race.

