Two specific papers have supported the use of Bismuth as a treatment option for COV+. [name] (Hong Kong) found that Bismuth was effective in inhibiting the SARS Corona virus helicase. Of note, this potential efficacy was noted by the Jinyintan Hospital during the current COV-19 pandemic. After several of their staff were infected, they used bismuth compounds prophylactically and noted no further infections.

These data point to the efficacy of preventing viral enteritis and low risk-profile for patients treated with BSS. Clearly, BSS may be part of a strategy for COV+ treatment given its low therapeutic risk profile and documented gut-virus clinical efficacy.

2. Study Objectives

The objectives of this pilot study are: To evaluate the tolerance and efficacy of BSS and SOC in mild/moderate severity COV+ population as defined by QRT-PCR of saliva or nasal swab samples compared to SOC and placebo and compare this efficacy to patients treated with SOC (placebo) alone. This will first be tested in 10 open-label patients, then in 2 groups of 25 patients as follows: Group one with mild/moderate disease and Group 2, patients with mild/moderate disease and persistently positive

for the SARS-Cov-2 virus by QRT-PCR testing for 14 days or more. This study is to assess the potential for BSS to influence the gut as a reservoir of infection by the SARS-Cov-2 virus and to determine the primary effect objective of change in stool frequency of patients treated with BSS compared to placebo treated patients.

Primary efficacy objective:

To determine whether treatment with BSS of Mild/Moderate COV+ decreases mean daily stool frequency compared to placebo-controlled patients

Secondary efficacy objectives:

Duration of hospitalization in BSS compared to PBO treated groups.

Weight gain (and BMI) relative to baseline at Week 1, and through Week 2.

Stool microbiota at baseline and Week 1, and through Week 2 (to be analysed at a later date).

To determine whether treatment with BSS of Mild/Moderate COV+ decreases the time to viral clearance (negative test by daily saliva testing) and persistently COV+ testing patients (over 14 days of COV+ testing) with Mild/Moderate disease, time until negative test by daily Saliva test.

3. Investigational Plan

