3.1 Study Design

This will be a 3 week, randomized, single-center, double-blind, proof-of-concept (POC) pilot study to evaluate the efficacy of patients with mild-moderate COVID-19+ infection. There will be an initial 10-pateint open-label study to assess patient tolerance to the active treatment arm of the study. The first 10 open-label patients will be treated with BSS 2 tablets PO (to chew) up to 4 times daily for 3 days (72 hours). The second 2 groups of patients will be mild (at home) or moderate (hospitalized, not on a ventilator) COV+ testing or with persistently + COVID testing for 14 days or more.

Patients will be allowed to receive a SOC treatment regimen at baseline (Appendix 2)

Standard of care (which includes any non-excluded SOC medications).

This pilot study will be conducted in the US in 1 center. A total of 60 patients are expected to be enrolled into the 3 arms of the study. Study one will consist of 10 open label COV+ patients with mild/moderate disease, the second and third studies will be double-blind placebo controlled studies of 25 patients each, the first with Mild/Moderate disease upon diagnosis by QRT-PCR+ testing and the third will consist of patients who are COV+, mild to moderate in severity with documented COV+ status by QRT-PCR testing for 14 days or more.

Screening will occur at the time patients are diagnosed via QRT-PCR testing. This may occur at one of several locations and/or time points of diagnosis:

- emergency room [ER]
- physician's office on the U of L campus.
- · University of Louisville hospitals (ULH Main and Jewish facilities).
- · Selected parking lot on UL campus.

 Campus Health (patients/students may be recruited via Practitioners or by approved recruitment flyers

Patients with initial COV+ confirmed by QRT-PCR testing will be approached to provide informed consent for the study. A third group of patients will be recruited with persistently + QRT-PCR testing for 14 days or more (see table 2).

Randomization will occur during SOC treatment.

Visits will occur at Baseline (Day 1) when patients will receive their first dose of study drug (BSS or PBO), and daily during the study until the patient tests COV- by saliva test or 21 days, whichever comes first.

The study design is depicted in Appendix 2.

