3.2 Selection of Study Population

3.2.1 Inclusion Criteria

To be eligible to participate in the study, patients must meet the following criteria:

- Ability to provide written or remote informed consent (telephone and DocuSign)
- Ability to comply with study requirements,
- Men or women 18 to 85 years of age, inclusive
- Current diagnosis of an initial occurrence of non-severe, non-complicated COV+ infection as defined by:
 - Presence COVID-19 in the saliva or nasal cavity using POC QRT-PCR assay or, in study #3, documented COV+ status for 14 days or more.
 - Management in an outpatient (i.e., non-hospital) or inpatient setting NOT on a ventilator.
 - Alert and awake
 - · Able to chew the study drug completely.
 - Women should fulfill one of the following criteria:
 - Answer in the affirmative that "they are not or could not be pregnant"
 - Post-menopausal; either amenorrhea ≥12 months or follicle stimulating hormone >20 mIU/mL
 - Surgically sterile; hysterectomy, bilateral oophorectomy, or tubal ligation.
 - Women of childbearing potential participating in heterosexual sexual relations must be willing to use adequate contraception from Screening through the 21 Day visit, per Section 10.2.

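### The SAP makes saliva-negative rates primary although the stated primary objective is stool frequency versus placebo, and it is inconsistent about the comparator

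*Combined protocol and SAP*

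**What the plan says.** Section 2 (Study Objectives) states the primary aim twice. The opening paragraph says the study is to "determine the primary effect objective of change in stool frequency of patients treated with BSS compared to placebo treated patients". The primary efficacy objective then reads "To determine whether treatment with BSS of Mild/Moderate COV+ decreases mean daily stool frequency compared to placebo-controlled patients". Time to a negative saliva test is placed under the secondary efficacy objectives. Section 1 gives stool frequency as the study's main interest when explaining why no IND is sought.

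Section 3.1 sets out a concurrent control: "the second and third studies will be double-blind placebo controlled studies of 25 patients each". Sections 3.5.1 and 3.5.2 describe randomisation to BSS or placebo in both groups.

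The SAP in Section 3.6.1 says: "The primary efficacy analyses will be to compare the negative Saliva rates at Week 1, 2 and 3 between the SOC control group", set against BSS plus SOC, by ANOVA with baseline BMI as a covariate. It adds "Clinical factors such as age, antibiotic use, number of recurrences, etc. will be examined for the impact on the treatment effect". The next paragraph says "The analyses of the primary efficacy endpoint will be conducted to compare historical SOC control vs. BSS plus SOC groups", and then refers to comparing recurrence rates at each time point. A later sentence assigns continuous endpoints in general to ANOVA or a nonparametric alternative.

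**The concern.** The objectives and the analysis plan name different primary outcomes, and both are current text. The SAP's second paragraph also brings in a control that is not part of the design. The trial randomises and blinds so that BSS and placebo patients are comparable. A comparison with historical patients would give up that protection, and the documents identify no historical data set and no way of matching to one.

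At stake is what decides the trial. If the SAP is followed literally, the outcome ranked secondary in Section 2 becomes the headline result. If it is not, outcome and comparator can be settled after the data are seen.

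**Working it through.** The plan gives no alpha, power, effect size or standard deviation, so there is no sample-size figure to reproduce. The enrolment total is consistent: 10 + 25 + 25 = 60, of whom 25 + 25 = 50 are randomised. The rest of the check sets the sections side by side.

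**1. Outcome and comparator by section**

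| Section | Outcome | Status given | Comparator |
|---|---|---|---|
| 1 | Stool frequency | Main interest | None named |
| 2 | Stool frequency (change; daily mean) | Primary | Placebo |
| 2 | Time to viral clearance | Secondary | None named beside it |
| 3.4.2 | Stool frequency, time to negative test, adverse events | Unranked list | Placebo (for stool frequency) |
| 3.6.1, first paragraph | Saliva-negative rate, Weeks 1, 2 and 3 | Primary | SOC control group |
| 3.6.1, second paragraph | Primary endpoint, then recurrence rates | Endpoint called primary; recurrence not ranked | Historical SOC control |

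Two outcomes are expressly called primary: stool frequency and the saliva-negative rate. Two comparators are possible: concurrent placebo and historical SOC.

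**2. Word counts in Section 3.6.1.** Stool: 0. Placebo or PBO: 0. Historical: 1. Recurrence or recurrences: 2. Specified primary analyses of stool frequency: 0. The zero for placebo is weaker evidence than the zero for stool, because the SAP may be using SOC control to mean placebo plus SOC.

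**3. Size of the concurrent control.** Under the split in Section 3.5.2, placebo is 5 + 5 = 10 and BSS is 20 + 20 = 40, of 50. Section 3.5.1 gives a coin toss but also allows another randomising method. If the coin is used and is fair, the expected placebo count is 50 × 0.5 = 25, with a central 95% binomial range of 18 to 32. So the randomised control could be as small as 10, and its size is not settled.

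**4. Recurrence.** It appears in no objective (Section 2), efficacy assessment (Section 3.4.2) or schedule row (Appendix 1), and it is not defined. As a patient factor it has nothing to measure for earlier episodes, because Section 3.2.1 requires "Current diagnosis of an initial occurrence of non-severe, non-complicated COV+ infection as defined by". The number of prior recurrences is then 0 for every eligible patient.

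**5. Can one model serve both wordings in Section 2?** Let y be mean daily stool frequency in the window, b the baseline, and T the treatment indicator.

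- Model for the mean: y = α + τT + βb + error.
- Subtract b from both sides: y − b = α + τT + (β − 1)b + error.

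The treatment effect τ is the same. With a linear model and the same baseline in both, the change and daily-mean wordings need only one analysis. This does not carry over to a rank-based test.

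**6. Are the data assured?** Stool frequency is asked at screening (Section 3.4.1.1) and recorded on Day 1 (Section 3.4.1.2). After that, Section 3.4.1.3 says daily visits may occur, and Appendix 1 marks the Day 2–21 column optional. A window mean cannot rely on those counts as the plan stands. Section 3.1 also ends visits at a negative saliva test, so counts can stop at different times for reasons linked to the infection.

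**The case against.** Several points on the other side are fair.

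- *The SAP does cover stool frequency.* A reader might infer that it would go unanalysed. The documents do not support that: the sentence on continuous endpoints can reach it. But that sentence does not make it primary, gives no window, covariates or missing-data rule, and leaves the choice of method open.
- *The control may be the placebo arm.* A reader might infer that the SAP plainly replaces placebo with historical patients. That is too strong. Section 2 uses SOC with placebo in brackets for the control, so the SAP's first paragraph can mean the concurrent arm. The word historical occurs once, and nothing says placebo data would be discarded. What stands is that the SAP contradicts itself on the comparator for its primary endpoint.
- *Section 3.4.2 does not rank stool frequency as primary.* Correct. It is a list without order of importance. The ranking rests on Section 2, with support from Section 1.
- *Recurrence might be observed.* Section 3.1 ends visits at the first negative test, but Section 3.4.1.3 is looser and Appendix 1 has unscheduled visits. So recurrence is not strictly unobservable. It is undefined and tied to no objective.
- *This is a pilot.* That limits the consequences. It does not remove the need for the analysis plan to address the stated primary objective.

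**Conclusion.** The concern holds in this form. Section 2 makes stool frequency versus placebo primary, and Section 3.6.1 makes saliva-negative rates primary without naming stool frequency. No other section resolves the difference. The SAP is also inconsistent on whether its primary endpoint is compared with a concurrent or a historical control. As written, the stated primary objective would not be tested as primary, and the primary endpoint could be judged against non-randomised patients.

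The size is a matter of counts: two primary outcomes, two possible comparators and no specified primary analysis of stool frequency. These rest on the text alone. Only the figure of about 25 placebo patients needs an assumption, that a fair coin is used; under Section 3.5.2 the number is 10. The correction must be made before any outcome data are analysed.

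**What to change.** Rewrite Section 3.6.1 with one primary analysis.

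- **Outcome and comparison:** mean daily stool frequency, BSS versus concurrent randomised placebo.
- **Population:** the 50 randomised patients. Exclude the 10 open-label patients and describe them separately.
- **Window and baseline:** one prespecified window, for example the first treatment week, which fits the weekly unit in Section 3.4.2. State one baseline, either the screening history or a Day 1 pre-dose count.
- **Model:** ANCOVA on baseline stool frequency and study group (newly diagnosed or persistently positive) is one suitable choice. State whether the SAP's BMI covariate is kept. Add a rank-based or exact sensitivity analysis, since there may be only 10 placebo patients.
- **Data:** make the self-reported count required on every day of the window, and align Section 3.4.1.3 and Appendix 1 with this.
- **Early negative tests:** state how days after a negative saliva test are handled and which effect is estimated. Under Section 3.5.2 treatment also runs only until a negative test, so counts continued beyond it would mix days on and off treatment.
- **Viral clearance:** make it secondary, as time to first negative saliva test compared between randomised arms, with weekly negative rates as supportive.
- **Stray text:** delete the historical control and both mentions of recurrence, or label any historical comparison as exploratory.

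The allocation statements in Sections 3.5.1 and 3.5.2 must be reconciled separately.

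The cost is a rewrite of one section, matching edits to the visit schedule and a few more self-reported counts per patient. No extra patients or assays are needed.

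### Section 3.6.1 defines no efficacy analysis set and has no cohort term, so it leaves open whether the 10 open-label patients count in the BSS arm

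*Combined protocol and SAP*

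**What the plan says.** Section 3.1 describes the whole enrolment: "A total of 60 patients are expected to be enrolled into the 3 arms of the study". One of those three sets is open-label. "The first 10 open-label patients will be treated with BSS" for 3 days, and the stated aim of that step is tolerance. Section 3.5.1 then says: "The Subsequent 50 patients (two groups of 25) will be randomized to either placebo or BSS". Section 3.5.2 gives each randomised cohort 20 BSS and 5 placebo patients, treated for up to 21 days or until they test negative.

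Section 3.6.1 makes the primary comparison "between the SOC control group and the BSS + SOC treatment groups". For the model, it names an ANOVA whose only terms are treatment and BMI at baseline. It adds: "Clinical factors such as age, antibiotic use, number of recurrences, etc. will be examined for the impact on the treatment effect". Cohort is not in that list. The comparison is then restated as one to "compare historical SOC control vs. BSS plus SOC groups". The only population defined is for safety: "Intent-to-treat (ITT) patients who receive one dose of study drug will be included in the safety evaluation".

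**The concern.** The efficacy plan speaks of BSS groups in the plural without saying which they are. Three sets of patients receive BSS, and one of them was not randomised, was not blinded, was enrolled first and was treated for 3 days. If that set is counted in the active arm, part of the BSS-placebo difference no longer comes from randomisation. If the choice is left until the data are in, the analyst can pick either set.

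The second gap is cohort. Newly diagnosed patients and patients already positive for 14 days or more may well reach a negative test at different rates, and patients are allocated within these cohorts. The stated model has no term for cohort.

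**Working it through.** **1. The plan's own total.** 10 open-label + 25 + 25 = 60. This matches Section 3.1 and shows that the open-label set is one of the three arms counted there. The documents give no alpha, power or effect size, so no sample-size figure can be reproduced.

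**2. Composition of the BSS arm under 20:5 (Section 3.5.2).**
- Randomised patients only: BSS 20 + 20 = 40; placebo 5 + 5 = 10.
- Open-label patients added: BSS 40 + 10 = 50; placebo 10. Open-label share = 10/50 = 20%.

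**3. Shift in the BSS rate if they are pooled.** Shift = open-label share × (open-label rate − randomised BSS rate). The rate differences are assumptions.

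| Assumed difference (points) | Shift at 20:5, share 10/50 | Shift if the coin toss gave 25:25, share 10/35 |
|---|---|---|
| 10 | 2.0 | 2.9 |
| 20 | 4.0 | 5.7 |
| 30 | 6.0 | 8.6 |
| 50 | 10.0 | 14.3 |

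Case mix alone could produce such a difference. Suppose all 10 open-label patients were newly diagnosed (an assumption). At 20:5 the newly diagnosed share of the BSS arm rises from 20/40 = 50% to 30/50 = 60%, against 5/10 = 50% on placebo. An assumed gap between cohorts of 20, 40 or 60 points then adds 0.10 × gap = 2, 4 or 6 points. This is one route to the shifts in the table, not an addition to them.

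**4. Effect on a test at 20:5.** Assumptions: no drug effect, negative rate 0.30, two-sided Fisher test at 0.05, exact enumeration.
- 40 vs 10, randomised only: rejection probability 3.4%.
- 50 vs 10, open-label rate also 0.30: 3.1%.
- 50 vs 10, open-label rate 0.80: 5.5%.
- 50 vs 10, open-label rate 1.00: 8.4%.

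Test size rises above 5% only when the open-label patients are very different. The main harm is to the estimate.

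**5. Leaving out cohort, taken separately for each allocation rule.**
- *20:5 in both cohorts.* The placebo share is 5/25 = 20% in each. Both arms have the same cohort mix, so leaving out cohort does not bias the randomised contrast. It leaves between-cohort variation in the error term and so costs precision.
- *Fair coin (Section 3.5.1).* Let X1 and X2 be the placebo counts, each Binomial(25, 0.5). Placebo shares differ by 20 points or more when |X1 − X2| ≥ 5. Because X1 + 25 − X2 is Binomial(50, 0.5), the probability is 2 × P(Binomial(50, 0.5) ≤ 20) = 0.203, or about 20% of trials. As an example, take 15 placebo patients in one cohort and 10 in the other. That cohort then makes up 15/25 = 60% of placebo and 10/25 = 40% of BSS. An assumed gap between cohorts of 20, 40 or 60 points puts the unadjusted contrast off by 0.20 × gap = 4, 8 or 12 points. A cohort term adjusts for this.

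The two rules do not agree: a fair coin gives exactly 20 of 25 on BSS with probability 0.0016. Sections 3.5.1 and 3.5.2 must be reconciled.

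**The case against.** A reader might infer that the plan intends to pool the open-label patients. The documents do not support that. Section 3.1 calls the three sets separate studies, describes only the second and third as placebo-controlled, and gives tolerance as the purpose of the first. The primary objective in Section 2 and the stool-frequency assessment in Section 3.4.2 are framed as BSS against placebo. Sections 2 and 3.5.1 also speak of two groups of 25, so the plural in 3.6.1 could mean just the two randomised BSS groups. It is also unclear whether patients treated for 72 hours would have saliva results at Weeks 1, 2 and 3, since Appendix 1 has no separate open-label schedule.

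This stands as an argument against a stated plan to pool. It does not close the gap, because other text points the other way. Section 3.5.1 assigns the first 10 to the treatment group, the table in 3.5.2 lists them under that heading, and Section 2 says that the evaluation of tolerance and efficacy is tested first in them. No sentence excludes them from efficacy.

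A reader might also infer that leaving out cohort confounds the treatment effect. Under 20:5 it does not, and under a coin toss the imbalance is chance rather than systematic bias. Analysing the cohorts separately is a legitimate reading of Section 3.1, so the plan should not be forced into one pooled analysis.

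Finally, if the control really is historical, as the second statement in 3.6.1 has it, the comparison is not randomised whatever is done with the open-label patients. That is correct, and the fix has to deal with that sentence too.

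**Conclusion.** The point holds as a gap in the analysis plan. Section 3.6.1 does not say who is in the efficacy analysis, and its stated model leaves out cohort. Including the open-label patients is permitted by ambiguity; it is not a stated rule.

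If they were included at 20:5, they would make up 20% of the BSS arm, and the BSS rate would move by 2 to 10 points for assumed outcome differences of 10 to 50 points. The cohort omission is the smaller matter: a loss of precision at 20:5, and unadjusted chance imbalance of 20 points or more in about 20% of trials under a coin toss.

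All outcome rates, rate differences, the 0.05 level and the newly diagnosed status of the open-label patients are assumptions. The illustrations use negative-test rates because Section 3.6.1 does. Section 2 names stool frequency as the primary objective; that mismatch is a separate matter, and the gap described here applies to either endpoint.

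**What to change.** Put this in Section 3.6.1:

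> Efficacy comparisons of BSS with placebo use only the 50 randomised patients. Any analysis that combines the two cohorts includes cohort as a factor (stratum) alongside treatment and baseline BMI, and estimates are also shown for each cohort. The 10 open-label patients are summarised separately for tolerability.

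In the same section, delete or reconcile the sentence on a historical control, so that the control is the concurrent randomised placebo group. Otherwise the new wording and the old would contradict each other. Reconcile the allocation rules in Sections 3.5.1 and 3.5.2.

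The cost is wording, one extra model term, and a common-effect assumption for any combined estimate. The cohort-specific estimates let the reader judge that assumption. No new data are needed and no treatment changes.

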3.4.1.1 Screening Visit (Days -1 to 0)

Screening will occur at the time the diagnosis of COV+ is confirmed for the first study. For the second study, screening will occur at 2 weeks or more of documented COV+ status. During the screening visit

enrolled patients will be provided with a stool collection kit. Two patient groups will be studied: The following will be obtained to determine patient eligibility:

- a. Written or remote informed consent; (telephone and DocuSign)
- b. Demographic data;
- c. Medication history for the previous 30 days;
- d. Medical history including daily stool frequency;
- e. Social history (alcohol, tobacco, drugs);
- f. Height and Weight (which can be self-reported);
- g. Vital signs (temperature, pulse, blood oxygen saturation, blood pressure within 1 week of screening visit);
- h. Verbal affirmation that to the best of their knowledge they are not pregnant;
- i. Collection of serious, procedure-related non-treatment emergent AEs;
- Reminder for patients to avoid the use of protocol excluded medications for the duration of the study

All screening laboratory test results must be reviewed, signed, and dated by an Investigator when they are received (see list in Appendix 2).

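### The stated primary outcome, mean daily stool frequency, has no baseline-adjusted analysis, although a baseline stool frequency is already collected

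*Combined protocol and SAP*

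**What the plan says.** - **Objective.** The primary efficacy objective in Section 2 asks whether BSS "decreases mean daily stool frequency compared to placebo-controlled patients". Section 3.4.2 lists mean daily stool frequency first among the efficacy assessments.
- **Primary analysis.** Section 3.6.1 names a different endpoint: "The primary efficacy analyses will be to compare the negative Saliva rates at Week 1, 2 and 3". The model for that comparison is ANOVA "with treatment group and baseline BMI as a covariate variable in the model".
- **Other factors.** "Clinical factors such as age, antibiotic use, number of recurrences, etc. will be examined for the impact on the treatment effect". Neither baseline stool frequency nor cohort is named.
- **Stool frequency.** The only rule in Section 3.6.1 that reaches it is the general one: "For continuous endpoints, the ANOVA or a nonparametric method will be used, whichever is appropriate". No covariate is attached.
- **Data collected.** Section 3.4.1.1 takes "Medical history including daily stool frequency" at screening. Section 3.4.1.2 records stool frequency on Day 1 and Section 3.4.1.3 records it daily. Appendix 1 confirms the screening and Day 1 entries. Under Section 3.1 the first dose is given at the Day 1 visit.
- **Randomised patients.** "The Subsequent 50 patients (two groups of 25) will be randomized to either placebo or BSS" (Section 3.5.1). One group is newly diagnosed and the other has tested positive for at least 14 days. Section 3.6.1 does not say whether they are pooled.

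**The concern.** Diarrhoea is not an entry criterion (Section 3.2.1), and Section 1 cites gastrointestinal symptoms in up to 60% of patients in some studies. Patients may therefore enter with very different stool frequencies. An unadjusted comparison leaves all of that spread in the error term and lets a chance imbalance between arms pass into the estimated effect. The placebo arm may be as small as 5 per cohort (table in Section 3.5.2), so such an imbalance could be large.

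The t-tests of baseline comparability planned in Section 3.6.1 do not remedy this. They have little power at these numbers, and no action follows from their result. A prespecified covariate uses data the trial already collects.

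**Working it through.** **The plan's own figures.** There is no power calculation, effect size, SD or alpha to reproduce. Total enrolment checks: 10 + 25 + 25 = 60, of whom 50 are randomised.

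**Inputs from the documents.** Two blinded cohorts of 25. Allocation is 20 BSS to 5 placebo per cohort in the Section 3.5.2 table (40:10 if pooled). The coin toss in Section 3.5.1 implies about 25:25 if pooled.

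**Assumptions not in the documents.** Correlation r between baseline and on-treatment stool frequency of 0.2 to 0.7; two-sided alpha 0.05; no dropout; one equally precise mean per patient; effects in within-cohort SD units.

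**Step 1: unadjusted standard error,** √(1/n₁ + 1/n₀):
- 40:10: √(0.025 + 0.1) = 0.354 SD
- 25:25: √(0.04 + 0.04) = 0.283 SD
- 20:5, one cohort: √(0.05 + 0.2) = 0.50 SD

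**Step 2: gain from baseline adjustment.** The variance factor is 1 − r² and the equivalent sample-size multiplier is 1/(1 − r²). Power and detectable difference come from the noncentral t at 40:10 with no cohort difference. Degrees of freedom are 48 unadjusted and 46 with baseline and cohort.

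| r | 1 − r² | Multiplier | 50 patients worth | Detectable at 80% power | Power for 1 SD |
|---|---|---|---|---|---|
| unadjusted | 1.00 | 1.00 | 50 | 1.01 SD | 79% |
| 0.2 | 0.96 | 1.04 | 52 | 0.99 SD | 81% |
| 0.3 | 0.91 | 1.10 | 55 | 0.97 SD | 83% |
| 0.5 | 0.75 | 1.33 | 67 | 0.88 SD | 89% |
| 0.7 | 0.51 | 1.96 | 98 | 0.72 SD | 97% |

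The variance factor is the same at 25:25. There, power for 0.8 SD rises from 79% to 89% at r = 0.5. In one cohort of 20:5, the detectable difference at r = 0.5 falls from 1.46 to 1.27 SD, and power for 1 SD rises from 48% to 60%.

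**Step 3: cost of estimating the slope.** With a normally distributed covariate, the expected variance is multiplied by 1 + 1/(N − 4).
- N = 50: 1 + 1/46 = 1.022. The net factor is 0.96 × 1.022 = 0.98 at r = 0.2 and 0.51 × 1.022 = 0.52 at r = 0.7.
- N = 25: 1 + 1/21 = 1.048. The net factor is 0.96 × 1.048 = 1.01 at r = 0.2 (no gain) and 0.75 × 1.048 = 0.79 at r = 0.5.

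**Step 4: chance imbalance.** In a 20:5 cohort, the difference in baseline means has a standard error of 0.50 SD. An imbalance of that size shifts the unadjusted effect by r × 0.50, which is 0.25 SD at r = 0.5.

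**Step 5: cohort term, if pooled.** Ignoring a cohort difference of c SD inflates residual variance to 1 + c²/4. Including the term therefore multiplies variance by 1/(1 + c²/4): 1.00, 0.94 and 0.80 for c = 0, 0.5 and 1.

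**Step 6: change scores.** The narrative in Section 2 also speaks of a change in stool frequency. With equal variances, a change score has variance factor 2(1 − r): 1.6 at r = 0.2, 1.0 at 0.5 and 0.6 at 0.7. It is worse than no adjustment below r = 0.5, and its factor exceeds 1 − r² throughout the range.

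**The case against.** A reader might infer that the SAP adjusts stool frequency for BMI in place of its own baseline, and so spends a degree of freedom on an irrelevant covariate. The documents do not support this. The BMI model belongs to the saliva-rate comparison. Stool frequency has no covariate, and overwriting the BMI sentence would delete the only named model for saliva clearance.

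The strongest case against acting is that the size of the gain cannot be derived from the plan. Many patients may have near-normal counts. The screening value is taken as history, and the Day 1 count falls on the day of first dosing and may be partly post-dose. Each of these could lower r, and at r = 0.2 the net gain is about 2% when pooled and nil in a single cohort. This stands as a limit on the claimed size. It does not favour leaving the analysis unadjusted, because the worst case over the assumed range is a loss of about 1%.

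It is also said that the cohorts are described as separate studies (Section 3.1), so a cohort term may not apply. That stands, and the term is conditional on pooling. Finally, the list of factors to be examined is open-ended and could include baseline stool frequency. But an open list prespecifies nothing, and it concerns influences on the treatment effect, not the model for this outcome.

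**Conclusion.** The point holds in this form: the stated primary outcome has no baseline-adjusted analysis, although a baseline value is already collected. Over an assumed r of 0.2 to 0.7, adjustment lowers the variance of the treatment effect by about 4% to 49%, worth 1.04 to 1.96 times the patients. After the slope cost, the pooled reduction is about 2% to 48%.

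Two stronger readings are not supported. The upper figure is not a demonstrated loss, because r is not in the documents. The missing cohort term is not an error unless the cohorts are pooled. This is a worthwhile, low-cost improvement to a pilot, ranking below the mismatch between its stated objective and its primary analysis. The allocation conflict also moves absolute precision more than a weak covariate would (standard error 0.354 against 0.283 SD).

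**What to change.** Keep the saliva analysis and add to Section 3.6.1:

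> Mean daily stool frequency on treatment will be analysed by ANCOVA with treatment and pre-dose baseline daily stool frequency, plus cohort (newly diagnosed / positive 14 days or more) if the two cohorts are pooled; a rank-based ANCOVA will be used if residuals are clearly non-normal.

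State which record supplies the pre-dose baseline, and whether the cohorts are pooled. Settle the choice between ANCOVA and its rank-based form before unblinding. BMI is not needed in this model.

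The cost is a short SAP edit and about one degree of freedom per added term. No new data are needed if the screening value serves as baseline; using Day 1 requires the count to be clearly pre-dose.

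Reconcile separately the stool-frequency objective (Section 2) with the saliva-based primary analysis (Section 3.6.1), the coin toss (Section 3.5.1) with the 20:5 split (Section 3.5.2), and the historical control mentioned in Section 3.6.1 with the concurrent placebo arm. The added sentence assumes the concurrent placebo comparison.
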